4.1 Model Specification

- Fixed effects: group, time, group \times time interaction
- Random effects: cluster (care unit/ward) and participant
- Covariance structure: unstructured

The primary parameter of interest was the group \times time interaction term.

5. Handling of Clustered Data

Clustering at the care unit/ward level was accounted for through random effects in the mixed-effects models.

6. Handling of Missing Data

Missing outcome data were handled using multiple imputation (MI) under the missing-at-random (MAR) assumption.

Mixed-effects models were estimated using maximum likelihood methods, allowing inclusion of participants with incomplete outcome data.

7. Sensitivity Analyses

Sensitivity analyses were conducted to assess the robustness of findings under alternative missing data assumptions.

8. Statistical Software

All analyses were performed using IBM SPSS Statistics version 25.0 (IBM Corp., Armonk, NY, USA).

9. Statistical Significance

All statistical tests were two-tailed with a significance level of $\alpha = 0.05$.

10. Deviations from the Protocol

Any deviations from the pre-specified analysis plan were documented and justified prior to data analysis.

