8.3 Timing of Assessments

All outcomes were assessed at:

- Baseline (pre-intervention),
- End of intervention (week 3), and
- Follow-up at one month post-intervention (week 7).

9. Data Collection Procedures

Data were collected using standardized questionnaires administered by trained research assistants. All assessors were blinded to group allocation where feasible.

10. Sample Size

A total of 103 nursing assistants participated in the study:

- Control Group: 50 participants
- VR with Debriefing Group: 53 participants

11. Adverse Events

The intervention was educational and non-invasive. Adverse events were monitored throughout the study period using participant self-report and

investigator observation. No adverse events were observed or reported in either study group.

12. Ethics and Informed Consent

The study was conducted in accordance with ethical principles for research involving human participants. The study protocol was reviewed and approved by the Institutional Review Board of Taipei Medical University (TMU-JIRB approval number: N202203004). All procedures were conducted in accordance with relevant ethical guidelines and regulations. Written informed consent was obtained from all participants prior to participation.

13. Data Management and Confidentiality

All data were de-identified prior to analysis. Study data were securely stored and accessed only by authorized research personnel.

14. Limitations

Limitations of the study include the limited number of participating institutions, reliance on self-reported measures, a relatively short follow-up period, and the inability to blind participants due to the nature of the intervention.

15. Protocol Status

This protocol was prepared retrospectively for results reporting purposes. All reported analyses and outcomes reflect the procedures actually implemented in the completed study.

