Statistical Analysis Plan (SAP)

Title:

Effects of a Virtual Reality–Based Empathy Program on Empathy, Attitudes Toward Older Adults, and Empathic Behavior Among Nursing Assistants: A Cluster Randomized Controlled Trial

NCT No.: NCT07044492

Protocol Version: 4.0

Date: October 13, 2025

IRB Approval: Taipei Medical University Joint Institutional Review Board

IRB No.: N202203004

Principal Investigator: Principal Investigator (PI)

1. Analysis Population

All randomized participants with available outcome data were included in the analysis according to the intention-to-treat (ITT) principle.

2. Outcome Definition

The primary outcome was the empathy level score, and the secondary outcomes were attitudes toward older adults and empathic behavior; all outcomes were treated as continuous variables.

3. Descriptive Statistics

Baseline characteristics were summarized by group using:

- Mean and standard deviation for continuous variables
- Frequency and percentage for categorical variables

4. Primary Analysis

The primary analysis evaluated changes in empathy level, empathic behavior and attitudes toward older adults over time between groups using linear mixed-effects models (LMMs).

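### The primary contrast is a difference in change from baseline; holding the arms to a common baseline mean would be valid and somewhat more precise

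*SAP*

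**What the plan says.** SAP 4.1 gives the mean model as "Fixed effects: group, time, group" × time. It adds "Random effects: cluster (care unit/ward) and participant" and "Covariance structure: unstructured". On the test it says "The primary parameter of interest was the group" × time interaction. SAP section 4 describes the aim this way: "The primary analysis evaluated changes in empathy level, empathic behavior and attitudes toward older adults over time between groups".

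Protocol 8.3 ("All outcomes were assessed at") lists three time points for every scale. The first is "Baseline (pre-intervention"); the others are week 3 and week 7. Neither visit is named as primary.

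Neither document lists a baseline score as a covariate or holds the arms to a common baseline mean. The only other use of baseline data is descriptive (SAP section 3: "Baseline characteristics were summarized by group using").

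**The concern.** When baseline is a response visit and the group effect at baseline is free, the interaction at each follow-up compares the arms on change. A change score subtracts the whole baseline value, as if the slope of follow-up on baseline were 1. The slope is normally below 1, so a chance difference at baseline is over-corrected and the contrast carries avoidable variance.

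Randomisation gives the arms the same expected baseline, and this model does not use that fact. Precision is at stake. The trial has 103 participants in an unstated number of care units, Protocol section 6 describes no stratification or matching, and Protocol section 14 concedes that few institutions took part. The baseline scores needed to recover some of the loss are already in hand.

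**Working it through.** **Inputs from the documents.** Control 50, VR 53 (50 + 53 = 103, as stated in Protocol section 10); two-sided α = 0.05; three visits; random effects for cluster and participant. No power, effect size, SD, ICC, cluster size or correlation is given, so there is no planned figure to reproduce.

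**Assumptions.** Time is categorical and includes baseline. SDs are equal across visits. Variance components are treated as known. Clusters have m = 10 participants. The cluster effect is constant over visits, as the SAP's random intercept implies. Participant-level correlation ρ between visits is 0.3, 0.5 or 0.7. ICC is 0.05, 0.10 or 0.20.

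**Step 1: what the interaction estimates.** Group, categorical time and their interaction saturate the six arm-by-visit means. In complete data the interaction at a follow-up is therefore the difference in mean change, whatever the covariance structure. The unstructured covariance does not alter this.

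**Step 2: variance ratio.** Let r be the baseline-to-follow-up correlation of cluster means.
- Change contrast: proportional to 2(1 − r).
- Common-baseline contrast: proportional to 1 − r².
- Ratio: (1 − r²) / [2(1 − r)] = (1 + r)/2, below 1 for every r < 1.

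With a constant cluster effect, r = [m·ICC + (1 − ICC)·ρ] / [1 + (m − 1)·ICC].

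Example, ICC 0.05 and ρ = 0.5: r = (0.5 + 0.475)/1.45 = 0.672, ratio 0.836, SE reduction 1 − √0.836 = 8.6%.

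| ICC | Ratio at ρ = 0.3 / 0.5 / 0.7 | SE reduction |
|---|---|---|
| 0.05 | 0.77 / 0.84 / 0.90 | 12.2% / 8.6% / 5.0% |
| 0.10 | 0.83 / 0.88 / 0.93 | 8.7% / 6.1% / 3.6% |
| 0.20 | 0.90 / 0.93 / 0.96 | 5.1% / 3.6% / 2.2% |

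Exact generalised least squares with three visits and both random intercepts, fitted with free and with common baseline means, gave the same ratios at ICC 0.05 and 0.10, and also with no clustering (0.65, 0.75 and 0.85).

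**Step 3: upper bound, clustering ignored.** At ρ = 0.5 the ratio is 0.75. The difference detectable at 80% power is 2.80 × √(1/50 + 1/53) × SD factor, and the square root is 0.197. For change, the factor is √[2(1 − 0.5)] = 1, giving 0.55 SD. With a common baseline, the factor is √(1 − 0.25) = 0.866, giving 0.48 SD. A constant cluster effect raises r above ρ and so shrinks this gain.

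**Step 4: is a baseline covariate the same thing?** Not under clustering. A single participant-level slope is set mainly by variation within clusters, so it removes only part of a stable cluster effect, whereas the change contrast cancels that effect completely. With one follow-up visit and a pooled slope, the variance of the covariate-adjusted contrast over that of the change contrast is:

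| ICC | ρ = 0.3 / 0.5 / 0.7 |
|---|---|
| 0.05 | 0.82 / 0.87 / 0.92 |
| 0.10 | 0.99 / 0.99 / 0.99 |
| 0.20 | 1.34 / 1.22 / 1.12 |

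The covariate form gains less than the common-baseline form at every ICC shown, and at ICC 0.20 it is worse than the change analysis.

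**The case against.** The best defence is that the implemented test is sound. Under randomisation the difference in change is unbiased and its type I error is not inflated by this choice. That stands. A reader might infer from the regression-to-the-mean argument that the primary estimate is biased. The documents do not support that: over-correction applies conditionally on a chance imbalance and averages out over randomisations. Nor are the baseline scores discarded, since they enter as the first repeated response.

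A second defence is that the gain is modest and its size unknown. That also stands. A reader might take 25% less variance, equivalent to about a third more participants (1/0.75 = 1.33), as the cost to this trial. That figure assumes independent participants, and this is a cluster trial.

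Third, changing the primary model after the data are known would misdescribe what was done. Protocol section 15 says the document was written retrospectively and reflects the analyses carried out. This limits the remedy to an added, labelled analysis.

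Fourth, a common baseline mean is justified only if the arms share an expected baseline. In a cluster trial, allocation known before enrolment can influence who joins. Protocol sections 5 and 6 do not give the order of enrolment, baseline measurement and randomisation, so this must be checked.

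None of these removes the point that, in complete data, the free-baseline contrast is never more precise than the common-baseline one.

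**Conclusion.** The point holds as a loss of efficiency of modest size. The direction needs no assumed value: the ratio is below 1 for any r < 1, provided the baseline is unaffected by allocation. The size rests wholly on assumed values. With clusters of 10 and a constant cluster effect, the standard error would fall by about 2% to 12%, with the smaller gains at higher ICC and higher participant correlation. Very few clusters would add uncertainty in the variance components that these ratios ignore.

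The reading also depends on the SAP's time factor including baseline, which its language of change implies but does not state. If time covered only weeks 3 and 7, baseline would be unused and the interaction would not measure an effect from baseline.

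A reader might also expect a single week-7 result as the headline. The documents give weeks 3 and 7 equal standing, so both contrasts belong in the report.

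**What to change.** Add one model for each of JSE-HP, KAOP and empathic behavior. Keep all three visits as responses and keep the cluster and participant random effects. Hold the arms to a common baseline mean by dropping the group main effect at baseline, so that group enters only through its week-3 and week-7 terms. Report both adjusted differences with confidence intervals. Participants who lack a baseline score remain in this form.

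If a covariate form is used instead, include the cluster-mean baseline as well as the individual baseline, because a single participant-level slope can lose precision when the cluster effect is stable. This costs a cluster-level degree of freedom, which matters if clusters are few.

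Present the model beside the implemented analysis, labelled post hoc, and leave the SAP's account of what was done unchanged. Before fitting it, confirm and state that enrolment and baseline measurement could not have been influenced by cluster allocation; if that cannot be confirmed, say so and do not rely on the constraint. The cost is a short addition to the SAP and one re-run per scale on data already held.

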2.3 Hypothesis

Nursing assistants in the intervention group will show significantly higher

empathic behavior scores over time compared with the control group.

3. Study Design

This study was a two-arm, parallel-group, cluster randomized controlled trial (cluster RCT).

Clusters were defined as care building or floor level within long-term care institutions.

Eligible clusters were randomized in a 1:1 ratio to either:

- Virtual Reality (VR) with Structured Debriefing Group, or
- Control Group.

Outcome assessments were conducted at three time points:

- Baseline (pre-intervention),
- End of intervention (week 3), and
- Follow-up at one month post-intervention (week 7).

4. Study Setting

The study was conducted in long-term care institutions in Taiwan. Clusters were defined as care units at the building or floor level within institutions.

All interventions and outcome assessments were implemented within participating.

5. Participants

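### As listed, the random effects leave ward-level differences in change out of the primary group-by-time test, so the SAP's statement that clustering is handled is not supported for that parameter

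*SAP*

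**What the plan says.** Whole care units were randomised. Protocol Section 3 states "Clusters were defined as care building or floor level within long-term care institutions" and "Eligible clusters were randomized in a 1:1 ratio to either" of the two arms. I call these units wards. Protocol Section 10 gives 50 control and 53 VR participants, and Section 8.3 gives three assessments (baseline, week 3, week 7).

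SAP Section 4.1 has group, time and their interaction as fixed effects. It continues "Random effects: cluster (care unit/ward) and participant" and then "Covariance structure: unstructured", and it ends "The primary parameter of interest was the group \times time interaction term". It does not say whether the random effects are intercepts only, or which matrix is unstructured.

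SAP Section 5 concludes that "Clustering at the care unit/ward level was accounted for through random effects in the mixed-effects models". Section 6 specifies maximum likelihood. Section 7 limits sensitivity analyses to missing-data assumptions. Section 9 sets a two-sided 5% level. Neither document gives the number of clusters, an intracluster correlation or a degrees-of-freedom method.

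**The concern.** The interaction compares the arms on change within a person. A ward effect that is the same at every visit is subtracted out when change is formed, as is the participant effect. What remains is the within-person residual, and the model treats it as independent between colleagues on the same ward.

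Nursing assistants on one floor may share supervisors, debriefing facilitators and local events, so their scores could move together. A random effect for ward level does not capture that; a ward-by-time effect would. Without one, the confidence interval for the interaction is too narrow and its p-value too small whenever wards differ in change, however large or small the ordinary ward-level variance is. Section 4 applies the same model to empathy, attitudes and empathic behaviour, so all three outcomes are affected.

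**Working it through.** The plan gives no power or design-effect figure to reproduce; only the total can be checked, and 50 + 53 = 103.

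**Inputs.** From the documents: 50 and 53 participants, three visits, two-sided 5% level. Assumed: number of clusters K (6, 8 or 16); ward-by-time share of visit-level residual variance ρ (2%, 4% or 10%); residual variance 0.5 for the standard-error illustration.

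**1. Does the ward intercept reach the interaction?** Write each score as fixed effects + ward u + participant p + residual e. In the change from baseline to week 7, u and p cancel, so

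Var(interaction) = 2σ²(1/50 + 1/53).

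With σ² = 0.5 this is 1 × 0.038868, and the SE is 0.19715. Exact generalised least squares with 4 wards per arm gives 0.19715 for ward-intercept variances of 0, 0.05, 0.2, 1 and 5. Over the same range the SE of the baseline group difference rises from 0.197 to 1.593. With an illustrative unstructured residual matrix, the interaction SEs (0.20677 at week 3, 0.24938 at week 7) are again unaffected by ward-intercept variance: that matrix describes correlation within a person, not between colleagues. With 30% of post-baseline visits missing, the week-7 SE moves only from 0.22438 to 0.22456, under 0.1%.

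**2. What does a ward-by-time effect add?** With variance ω² at each visit and k wards of about equal size per arm, the extra variance is 2ω²(1/k + 1/k). For k = 4 this equals ω². The SE becomes √(0.038868 + ω²): 0.221, 0.253, 0.298 and 0.373 for ω² = 0.01, 0.025, 0.05 and 0.10.

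**3. True type I error.** The intracluster correlation of change is ω²/(ω² + σ²) = ρ. With average ward size m = 103/K, the design effect is DE = 1 + (m − 1)ρ, and the true level of a nominal 5% test is about 2[1 − Φ(1.96/√DE)]. For K = 8 and ρ = 0.04: m = 12.875, DE = 1 + 11.875 × 0.04 = 1.475, 1.96/√1.475 = 1.614, giving 10.7%.

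The last column is a simulation under no effect (6,000 runs per cell, complete data, test of the week-7 contrast):

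| Clusters | ρ | DE | Formula | Simulated |
|---|---|---|---|---|
| 6 | 2% | 1.32 | 8.8% | 8.5% |
| 6 | 4% | 1.65 | 12.7% | 13.3% |
| 6 | 10% | 2.62 | 22.6% | 23.1% |
| 8 | 2% | 1.24 | 7.8% | 7.7% |
| 8 | 4% | 1.48 | 10.7% | 10.8% |
| 8 | 10% | 2.19 | 18.5% | 19.2% |
| 16 | 2% | 1.11 | 6.3% | 6.5% |
| 16 | 4% | 1.22 | 7.6% | 7.6% |
| 16 | 10% | 1.54 | 11.5% | 11.5% |

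At ρ = 0 the planned test holds its level (4.7% to 5.5%). The joint 2-df interaction test is worse: 8.8%, 13.2% and 26.0% with 8 clusters.

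**4. Do the remedies work?** A t-test on ward mean changes with K − 2 df stayed at 4.5% to 5.5%. A cluster-by-time effect fitted by maximum likelihood, with cluster-based df and a balanced approximation, still gave 2-df type I errors of 9.9% and 10.8% with 6 clusters (ρ = 4%, 10%), and 8.2% and 9.1% with 8. At ρ = 4% with 8 clusters, maximum likelihood set the ward-by-time variance to zero in 42% of runs, which brings back the unadjusted test. REML gave about 5%.

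**The case against.** The strongest objection is that Section 4.1 never says the random effects are intercepts. An unstructured covariance has no content for a single scalar ward effect, so the line refers either to the repeated-measures residuals or to a random-effects matrix with several terms. If the latter includes ward-level time effects, nothing cancels and Section 5 is right. This stands as a real ambiguity. Intercepts only is the plainer reading because no time-varying ward term is listed, but the text does not settle it, and the point is conditional on it.

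Second, removing stable ward differences is legitimate, since each participant is compared with their own baseline. This stands in full. A reader might infer that the primary test ignores ward clustering altogether. The documents do not support that: only ward-level variation in change is left out, and the test is valid if that variation is zero.

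Third, the size is assumed. Neither the number of clusters nor any correlation is given, so a reader should not conclude that the reported p-value is wrong, or by how much. This stands too.

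Fourth, the simulated column pools the residual over visits, with 2 × (103 − 2) = 202 df. That assumes compound symmetry. With unstructured residuals a single contrast has about 103 − 2 = 101 df. This limits any claim to reproduce the planned model exactly, but both counts are based on participants rather than wards, and the formula column does not depend on either.

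**Conclusion.** The point holds conditionally. If the random effects are intercepts, the ward term contributes nothing to the precision of the primary parameter (exactly with complete data, almost exactly with missing visits). Section 5's assurance then applies to arm means at a single visit but not to the interaction.

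The consequence is possible inflation of unknown size. The tabulated range, from 6.5% to 23.1% for the week-7 contrast, rests on assumed cluster numbers of 6 to 16 and assumed ward-by-time shares of 2% to 10%. The inflation disappears at zero share. Because this concerns the primary inference of a trial that randomised whole wards, and no other analysis in the SAP checks it, it needs resolving before the result is relied on.

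**What to change.** State in SAP Section 4.1 which random terms were fitted, which matrix was unstructured, how many clusters there were, and which degrees-of-freedom method was used. If ward-level time effects were in the model, saying so closes the modelling gap.

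Otherwise, choose one of two routes:

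- Base the primary inference on ward mean changes, compared between arms with K − 2 df. This held its level in simulation.
- Add a random cluster-by-time effect, estimated by REML rather than maximum likelihood, with Satterthwaite or Kenward-Roger df where the software allows. Adding the term while keeping the maximum likelihood of Section 6 is not enough with few clusters.

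Re-run the primary result on the existing data and correct Sections 4.1, 5 and 6 to match. For the ward-level route, state how missing visits enter the ward means.

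The work is a single re-analysis; Protocol Section 15 confirms that the study is complete. The price is a wider confidence interval and fewer degrees of freedom. The two-sided 5% critical value with K − 2 df is 2.78 for 6 clusters, 2.45 for 8 and 2.14 for 16, against 1.96 for a normal test.

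### Maximum likelihood with no small-sample degrees of freedom makes comparisons that carry cluster variance too liberal if clusters are few; the primary group-by-time test as listed is only slightly affected

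*SAP*

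**What the plan says.** SAP section 6 gives the estimation method: "Mixed-effects models were estimated using maximum likelihood methods". The reason it offers is that people with some outcome values missing can be kept in the analysis. The same section also specifies multiple imputation. REML is neither named nor ruled out. No df method appears in either document, and SAP section 8 names the software but not its settings.

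SAP section 4.1 defines the model. The random part reads "Random effects: cluster (care unit/ward) and participant", followed by "Covariance structure: unstructured", without saying whether this applies to the residuals or to the random effects. The target is stated: "The primary parameter of interest was the group \times time interaction term". SAP section 9 sets two-sided testing at 0.05.

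On size, Protocol section 10 says "A total of 103 nursing assistants participated in the study" (50 control, 53 intervention). Protocol section 3 randomises care units, at building or floor level, 1:1. The number of units is not given. The nearest indication is Protocol section 14: "Limitations of the study include the limited number of participating institutions".

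**The concern.** ML estimates variance components as if the fixed effects were known. In a cluster-randomised trial the arm effect is estimated from K cluster means, so ignoring the two df spent on the arm means matters when K is small. The cluster variance comes out too low, standard errors of between-arm comparisons are too small, intervals are too narrow and p-values too small. Using a normal or large-df reference instead of one tied to K makes it worse.

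The SAP's reason for ML does not require it. REML uses the same incomplete records under the same missing-at-random assumption. What is at stake is the validity of any arm difference at week 3 or week 7 taken from these models, and of the group-by-time test if the fitted model lets cluster effects change over time.

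**Working it through.** The documents give no power, intraclass correlation (ICC) or K, so there is no stated figure to reproduce. The participant counts do add up (50 + 53 = 103).

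**Inputs.** From the documents: N = 103, three time points, two arms, alpha = 0.05 two-sided. Assumed: K = 6 to 20 (30 as a check), equal cluster sizes, complete data. For the simulations also: cluster ICC 0.05 to 0.10 and, in the second, within-person correlation 0.6.

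**1. Contrast carrying cluster variance, estimate above zero.** ML divides the between-cluster sum of squares by K, REML by K-2. The ML variance is therefore (K-2)/K of REML, and the standard error is too small by the factor sqrt((K-2)/K). Actual type I error is P(|t(K-2)| > c × sqrt((K-2)/K)), with c the t(K-2) critical value or 1.96.

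| K | variance too low by | t(K-2) critical value × factor | error, t(K-2) | error, normal |
|---|---|---|---|---|
| 6 | 33% | 2.776 × 0.816 = 2.267 | 8.6% | 18.5% |
| 8 | 25% | 2.447 × 0.866 = 2.119 | 7.8% | 14.1% |
| 12 | 17% | 2.228 × 0.913 = 2.034 | 6.9% | 10.4% |
| 20 | 10% | 2.101 × 0.949 = 1.993 | 6.2% | 7.9% |

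At K = 30 the errors are 5.8% and 6.9%. REML with t(K-2) gives 5.0% throughout.

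**2. Allowing the variance estimate to be truncated at zero.** One-visit simulation, N = 103, 40,000 trials per cell, t(K-2) reference or t(N-2) when truncated. ML: 8.0 to 9.0% (K = 6), 6.8 to 7.6% (K = 8), 5.9 to 6.5% (K = 12). REML: 4.5 to 5.3%. The df rule matters. In a three-visit simulation (6,000 trials per cell) of the group main effect, with K-2 df kept even when the estimate is zero, ML at K = 6 gave 4.1% at ICC 0.05 and 6.3% at ICC 0.10. With a normal reference it gave 12.6% and 16.1%.

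**3. Primary group-by-time test, random intercepts as listed.** Cluster and participant intercepts cancel from within-person change, so K drops out.
- Residual df = 103 × 2 - 2 (time) - 2 (interaction) = 202; the ML divisor is 206.
- One-df test, normal reference: 1.96 × sqrt(202/206) = 1.941 on t(202), error 5.4%.
- Two-df chi-square test: (5.991/2) × 202/206 = 2.938 on F(2,202), error 5.5%.
- Unstructured participant covariance (df 101, divisor 103): one-df error 5.5%. For two df, 5.991 × 101/103 = 5.875, then 5.875 × 100/(2 × 101) = 2.908 on F(2,100), error 5.9%.

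**4. Cluster effects that drift while the model has intercepts only.** Three-visit simulation, ICC 0.05, 20% of cluster variance time-varying. Error of the interaction test:

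| K | ML | REML |
|---|---|---|
| 6 | 10.3% | 9.6% |
| 10 | 8.3% | 7.8% |
| 20 | 6.4% | 5.9% |

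Most of the excess comes from the omitted term, not the estimator. A cluster-level analysis of change with K-2 df stayed between 4.7% and 5.4% in all settings.

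**The case against.** The strongest reply is that the designated test hardly moves. Group by time is the stated target, the listed random effects read naturally as intercepts, and step 3 gives 5.4 to 5.9% whatever K is. The SAP specifies no separate test of arm differences at week 3 or week 7. This stands, and it limits the point to comparisons that carry cluster variance. It does not remove it: group is a fixed effect in the model, visit-specific arm differences are an obvious by-product, and the unclear covariance line leaves open whether cluster effects may vary over time.

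K is also unknown. Protocol section 14 speaks of institutions, and one institution can supply several buildings or floors. A reader might infer that clusters are few; the documents do not establish it. With a t reference the error at K = 20 to 30 is only 6.2 to 5.8%.

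The wording about likelihood methods is plural and sits in a missing-data section, so REML is not excluded, although full ML is the natural reading. If REML was used, one sentence settles that part.

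Finally, the largest figures in step 1 combine ML with a normal reference, which the SAP does not specify. They are an upper case, not the effect of ML alone.

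**Conclusion.** The point holds for tests and intervals that carry cluster variance: arm differences at week 3 or week 7, and group by time if a cluster-by-time or cluster-slope effect is in the model. There, full ML gives type I error of about 8.6% to 6.2% over assumed K = 6 to 20 with a t(K-2) reference, and more with a normal one. These figures assume balance, complete data and an estimate above zero; near zero the result depends on the df rule.

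Two stronger readings are not supported. A reader might infer that the primary result is seriously inflated by ML; with the random intercepts as listed it is not. A reader might also infer that REML with small-sample df cures the clustering problem without cost. It corrects only variance terms that are in the model, and intervals widen.

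**What to change.** Refit the models by REML with Satterthwaite or Kenward-Roger df for all group and group-by-time tests. If multiple imputation is used, combine the df properly over imputations; the df of a single fit is not enough. Report clusters per arm and the df with each p-value, and state whether the completed analysis used ML or REML and what the unstructured covariance refers to.

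Protocol section 15 says the document was written retrospectively and reflects what was done. The refit should therefore appear beside the original results, labelled as an added analysis. The SAP should not be reworded as if REML had been used.

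The refit does not replace a cluster-by-time effect. That term, or a cluster-level analysis of change, is a separate addition worth making as a sensitivity analysis.

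Cost: a modest re-analysis, no new data and no loss of incomplete records. For contrasts that carry cluster variance, intervals widen by sqrt(K/(K-2)) when both fits use t(K-2): 1.22 times at K = 6 and 1.05 at K = 20. Against ML with a normal reference they are about 1.7, 1.3 and 1.1 times as wide at K = 6, 10 and 20. That is the price of a valid test.
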